9.4.4 Pharmacokinetic Analyses

Analyses will be carried out on the PK analysis population. All PK parameters will be presented by listings and descriptive summary statistics (mean, standard deviation, coefficient of variation, median, minimum, and maximum) separately by dose levels and/or dosing regimen.

Individual and mean serum RO7121661 concentration versus time data will be tabulated and plotted by dose levels and/or dosing regimen. Graphical displays of PK data may also be provided. The serum PK of RO7121661 will be summarized by estimating total exposure (AUC), maximum concentration, total clearance, volume of distribution at steady-state, and terminal half-life (when applicable). Estimates for these parameters will be tabulated and summarized. Inter-participant variability and drug accumulation will be evaluated.

9.4.5 Immunogenicity Analyses

The immunogenicity analyses will include all participants with at least one ADA assessment, irrespective of whether or not the participant receives any treatment (Shankar et al 2014).

The numbers and proportions of ADA-positive participants and ADA-negative participants at baseline (baseline prevalence) and after study drug administration (post-baseline incidence during both the treatment and follow-up periods) will be summarized.

- Participants are considered to be ADA positive if they are ADA negative at baseline but develop an ADA response following study drug administration (treatment-induced ADA response), or if they are ADA positive at baseline and the titer of one or more post-baseline samples is greater than the titer of the baseline sample by a scientifically reasonable margin such as at least 4-fold (treatment-enhanced ADA response).
- Participants are considered to be ADA negative if they are ADA negative at baseline
 and all post-baseline samples are negative, or if they are ADA positive at baseline
 but do not have any post-baseline samples with a titer that is greater than the titer of
 the baseline sample by a scientifically reasonable margin such as at least 4-fold
 (treatment unaffected).

The relationship between ADA status and safety, efficacy, PK, and biomarker endpoints will be analyzed and reported descriptively via subgroup analyses.

9.4.6 Pharmacodynamic Analyses

The PD analysis will be based on the availability of evaluable blood or tumor samples. PD parameters will be listed by participant. Parameters may be tabulated by dose-level/regimen and time-point. Depending on findings, descriptive statistics may be used in summarizing relevant peripheral blood and tumor PD markers. Absolute change from baseline may be calculated for the PD markers. Graphical techniques may be employed to better understand the relationship of the PD markers with dose and time. Correlations

between PD markers, PK of RO7121661, and clinical response may be assessed through data tabulations and graphical techniques. The potential prognostic value of the PD markers may also be investigated.

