3. OBJECTIVES AND ENDPOINTS

The objectives and corresponding endpoints provided in Table 4, apply to:

- Part A: RO7121661 single agent dose escalation phase
- Part B: RO7121661 single agent expansion in selected indications

Table 4 Objectives and Endpoints

Objectives	Endpoints
Primary	
Dose Escalation: Safety, tolerability, MTD and/or RDE.	 Nature and frequency of DLTs and other AEs, PD and PK profile.
	 Incidence, nature and severity of AEs graded according to the National Cancer Institute (NCI) Common Terminology Criteria for Adverse Events (CTCAE) v5.0.
Expansion: Assessment of the anti-tumor activity of RO7121661.	 According to Response Evaluation Criteria in Solid Tumors (RECIST) Version 1.1 criteria:
	 Objective response rate (ORR).
	 Disease control rate (DCR); defined as ORR+stable disease rate (SDR).
	 Duration of response (DoR).
	 Progression free survival (PFS) defined as the time from the first study treatment (Day 1) to the first occurrence of progression per Investigator assessment or death from any cause, whichever occurs first.
Secondary	
To characterize the immunogenicity profile of RO7121661 (Part A and B).	Incidence of anti-drug antibodies (ADAs).
To explore potential PD-1, TIM-3 and PD-1/TIM-3 specific PD biomarkers (Part B).	 Examine the profile and status of T cell proliferation/activation in tumor biopsies and peripheral blood.
To investigate the single and multiple dose PK of RO7121661 (Part A and B).	 PK profiles and parameters derived for RO7121661.
To explore degree of target binding of RO7121661 (in association with PK/PD) via RO (Part A).	Evaluate RO via ex-vivo assay.
To evaluate the safety and tolerability of RO7121661 (Part B).	 Incidence, nature and severity of AEs graded according to the NCI CTCAE v5.0.
To explore preliminary anti-tumor activity of RO7121661 (Part A).	 According to RECIST Version 1.1 criteria: Objective response rate (ORR).
	 Disease control rate (DCR).
	 Progression-free survival (PFS).
	 Duration of response (DoR).

Table 4 Objectives and Endpoints (cont.)

Objectives	Endpoints
Tertiary/Exploratory	
To make a preliminary assessment of the anti-tumor activity of RO7121661 using immune-related RECIST (iRECIST) (Part A and B).	 Investigator-determined assessment using iRECIST:
	o ORR.
	 DCR; defined as response rate (RR)+stable disease (SD).
	o DoR.

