5. STUDY POPULATION

The study population rationale is provided in Section 4.3.1.

The study population consists of male and female participants with advanced and/or metastatic solid tumors.

Prospective approval of protocol deviations from recruitment and enrollment criteria, also known as protocol waivers or exemptions, is not permitted.

Participants enrolled in the study but who do not maintain eligibility or withdraw consent **prior to the first dose** will not be included in the database.

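### Section 9.4.5 requires only one ADA result, so participants with no post-baseline sample count as ADA negative and post-baseline incidence is slightly understated

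*Combined protocol and SAP*

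**What the plan says.** Section 9.4.5 of the combined protocol and SAP opens with the inclusion rule: "The immunogenicity analyses will include all participants with at least one ADA assessment, irrespective of whether or not the participant receives any treatment". It then asks for the numbers and proportions of ADA-positive and ADA-negative participants at baseline (prevalence) and after study drug (incidence over treatment and follow-up). No second denominator is given for incidence.

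A baseline-negative participant is ADA negative if, in addition, "and all post-baseline samples are negative". A baseline-positive participant is ADA negative if they "do not have any post-baseline samples with a titer that is greater than the titer of" the baseline sample by a reasonable margin, for which 4-fold is the example. There is no category for participants who cannot be evaluated. ADA status is then related descriptively to safety, efficacy, PK and biomarkers.

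Elsewhere:
- Table 4 (Section 3) lists ADA incidence as a secondary endpoint for both parts.
- Table 7 (Section 9.3) has no immunogenicity population. Its safety population is the default unless another set is specified, and requires one dose but no later sample. Its PK population requires a dose and a post-dose sample.
- Section 5 covers the time before the first dose: "Participants enrolled in the study but who do not maintain eligibility or withdraw consent" at that stage "will not be included in the database". Section 7.1 says the same of participants who withdraw before treatment starts.

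**The concern.** Prevalence and incidence need different denominators. Prevalence needs a baseline result. Incidence needs a baseline result and at least one result after exposure. A single set that asks for any one result leaves in the incidence denominator people who had no chance of entering the numerator, so the bias can only be downward.

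Two outputs are affected. The first is the secondary endpoint itself. The second is the comparison by ADA status: participants who died early, withdrew or missed their draws are classed as ADA negative because no sample exists. Their short follow-up and poor outcomes would then be attributed to the ADA-negative group, which could hide the loss of efficacy that Section 8.5.1 names as a possible consequence of ADA.

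**Working it through.** The plan states no ADA incidence, no number evaluable for ADA and no expected share without a post-baseline sample. There is therefore no figure to reproduce. The check has three parts.

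**1. Does the wording take in a participant who has only a baseline sample?**
- Baseline positive, nothing later: this person has no later sample with a raised titer, so the second limb of the ADA-negative definition is met literally.
- Baseline negative, nothing later: there is no later sample that fails to be negative, so the first limb is met by default.
- Neither limb, and no other section, removes such a participant.

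**2. How large is the effect?** Let N be the size of the set, f the share with no post-baseline sample, and p the incidence among those with at least one. Every ADA-positive participant must have a post-baseline sample, so

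reported incidence = p × N(1 − f) / N = p(1 − f).

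The relative shortfall is f and the absolute shortfall is p × f. Both p and f are assumptions:

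| p | f = 2% | f = 5% | f = 10% | f = 15% |
|---|---|---|---|---|
| 10% | 9.8% | 9.5% | 9.0% | 8.5% |
| 30% | 29.4% | 28.5% | 27.0% | 25.5% |

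The shortfall runs from 0.10 × 0.02 = 0.2 to 0.30 × 0.15 = 4.5 percentage points.

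In counts, take N = 270 (the lower end of planned enrolment, Section 9.2), p = 20% and f = 10%. Then 27 participants have no later sample and 243 do. About 0.20 × 243 = 48.6, or 49, are positive. The literal rule gives 49/270 = 18.1%; the evaluable denominator gives 49/243 = 20.2%.

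In a small dose cohort, f can be larger by chance. With three participants (the cohort size in the Appendix 10 mock runs), one of them baseline-only and one positive, the rule gives 1/3 instead of 1/2.

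**3. How large is f likely to be?** Tables 2 and 3 schedule the first ADA draw before dosing on Cycle 1 Day 1, then before dosing at Cycles 2, 3, 4 and 5 (Days 15, 29, 43 and 57 on schedule). They also schedule draws at early termination and safety follow-up. A participant ends with a baseline sample only through death, loss to follow-up, withdrawal of consent or missed draws before any of these. Section 7.2 stops all follow-up once consent is withdrawn, so f is not zero, but the schedule points to the low end of the assumed range.

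**The case against.** The best defence is that Section 9.4.5 says only who enters the immunogenicity analyses, and then separates status at baseline from status after study drug. An analyst could reasonably restrict the second proportion to participants with a post-baseline sample. The baseline-negative limb also reads most naturally as presuming that such samples exist. The rule carries a literature citation, and that source might supply an evaluable denominator. The endpoint is descriptive, with no hypothesis attached (Section 9.1). These points lower the stakes but do not repair the text: the restriction is not written down, the baseline-positive limb takes in these participants without any strained reading, and the plan should not depend on an outside source for a denominator.

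Three stronger readings are tempting and are not supported.

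- A reader might infer that untreated participants dilute the incidence. No ADA sample is scheduled before the Cycle 1 Day 1 pre-dose draw, and Sections 5 and 7.1 keep pre-dose drop-outs out of the database, so this group should be practically empty. Even 5 untreated participants added to 270 treated would move 20% only to 54/275 = 19.6%. What remains is a mismatch in wording between those sections and Section 9.4.5.
- A reader might infer that cohorts with early progression are hit hardest. The first scheduled scan is at 8 weeks ± 7 days (Table 1), after the Cycle 2, 3 and 4 draws. Earlier clinical progression leads to an early termination visit with an ADA draw. In Part A, DLT evaluability requires two doses, and ADA is drawn before the second.
- A reader might take the dilution as certain and material. It follows only if the rule is applied literally, and its size rests on an assumed f.

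**Conclusion.** The point holds as a minor error in a stated rule. Section 9.4.5 gives one set for two measures, no section supplies a post-baseline denominator, and the ADA-negative definition counts unevaluable participants as negative. Applied as written, post-baseline incidence is understated by the relative amount f, and the ADA-negative subgroup contains participants whose status is unknown. The direction follows from the text. The size does not: the 2% to 15% range for f and the 10% to 30% range for p are assumptions, and the sampling schedule makes a small f more likely. The clause admitting untreated participants is a wording inconsistency with almost no effect on the estimate.

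**What to change.** Replace the single set in Section 9.4.5 with two, and mirror them in Table 7:

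- Baseline prevalence: participants with a baseline ADA sample.
- Post-baseline incidence and all ADA-status subgroups: participants with at least one dose and at least one post-baseline ADA sample. This parallels the existing PK population.
- Report participants without a post-baseline sample as not evaluable, with their number by cohort.
- State how a participant with a post-baseline but no baseline sample is classified. Both current definitions depend on baseline status, so neither covers this case.
- Reconcile the clause admitting untreated participants with Sections 5 and 7.1.

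The change takes a few sentences and needs no new data or visits. It costs a slightly smaller denominator and gives a slightly higher reported incidence.

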- e) Blood for ADA determination of RO7121661 should be taken at indicated time-points up to Cycle 5. Thereafter, blood for ADA determination of RO7121661 will be taken at Cycle 7, Day 1, and every 6 cycles afterwards (Cycle 13, Cycle 19, Cycle 25, etc.). Blood for ADA determination should always be taken pre-dose.
- f) Participants with confirmed availability of representative archival tumor specimens in formalin-fixed, paraffin-embedded (FFPE) blocks (preferred) or unstained slides, with an associated pathology report.
- g) IgE and tryptase samples will be collected for central and local analysis if a participant experiences a Grade ≥2 IRR for the first time with the second or subsequent study drug infusion or with clinical signs of hypersensitivity reaction at any time of the conduct of the study. A second sample for central IgE/tryptase analysis will be collected approximately 48 hours after onset of the reaction.
- h) No biopsies are required in Part A dose escalation. If dose cohort is extended in Part A to confirm safety, PK and/or RO and/or the biomarker profile, then fresh tumor biopsies are mandatory for these additional participants, unless otherwise specified by the Sponsor. Screening sample should be collected after eligibility is confirmed. Post dose sample to be collected +2/-1 day[s] from scheduled timepoint.
- i) Samples for RBR DNA saliva will be collected on Day 1 from all participants who signed RBR ICF prior to study drug (RO7121661) infusion. If the RBR DNA saliva sample is not collected during the scheduled visit, it may be collected at any time during the conduct of the clinical study.
- j) Drug RO and PD-Plasma samples will be collected at Cycles 9, 22, 35 and 48.
- k) If sample is missed on Cycle, 1 Day 1, it can be collected at any time during the conduct of the study.
- After Cycle 5 the PD Serum sample should be collected every time a tumor assessment is done (every 8 weeks (\pm 7 days) thereafter for the first year; and every 12 weeks (\pm 7 days) thereafter until disease progression, treatment discontinuation or death).

Table 3 Schedule of Activities: Q2W regimen for Part B1, 2, 3, 4 and 5; hourly

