8.5 PHARMACOKINETICS

Mandatory blood samples to evaluate concentrations of study treatment will be collected from an IV line from the arm opposite to that used for study treatment administration. The date and time of each sample collection will be recorded in the eCRF. RO7121661 concentrations will be analyzed by using a validated assay. The PK samples will be taken as outlined in the SoA (see Section 1.3). During the course of the study, PK sampling time-points may be modified on the basis of emerging data to ensure the PK of RO7121661 can be adequately characterized (but without increasing overall blood collection volume for PK). This will be documented in a Note to File and a new SOA will be provided. Additional PK samples will be taken at the time of treatment discontinuation, if the participant experiences an infusion-related AE (such as an IRR), or if the participant experiences an AE leading to dose-reduction or delay of RO7121661 administration (see Section 6.6).

Remaining volumes of PK samples may also be used for additional PK/ADA analysis or assay development or validation, for RO7121661-related exploratory analyses, or to help develop further blood tests for exploratory analysis (e.g., further characterization of immune responses), after they are used for the mentioned intended use and as deemed appropriate.

The PK samples will be destroyed within 2 years after the date of final Clinical Study Report (CSR). Details on sampling procedures, sample storage, and shipment are given in the Study Flow Chart and Laboratory Manual.

8.5.1 Immunogenicity Assessments

Although RO7121661 is a human antibody, there is a risk that anti-drug antibody (ADA) against RO7121661 could develop, potentially reducing its efficacy and/or potentially resulting in symptomatic hypersensitivity reaction, in particular immune-complex reactions.

Antibodies to RO7121661 will be evaluated in blood samples collected from all participants according to the SoA (Section 1.3). Additional ADA samples should also be collected at the time of treatment discontinuation or at the safety follow-up visit and in participants who experience a Grade≥2 IRR and in participants with clinical signs of hypersensitivity reaction, in particular immune-complex reaction. In each case, for each collected ADA sample, a corresponding PK sample will be collected at the same time-point for the determination of the RO7121661 concentration.

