PFS will be defined as the time from study treatment initiation (Cycle 1 Day 1) to the first occurrence of documented disease progression (based on RECIST Version 1.1 Investigator's assessment) or death from any cause, whichever occurs first. For

participants who do not have documented progressive disease or death during the study, PFS will be censored at the day of the last tumor assessment.

Sensitivity analyses of response endpoints (ORR, DRC, DoR, and PFS) may include the evaluation of response according to iRECIST.

OS is defined as the time from the first dose of study treatment to the time of death from any cause. Participants who are still alive at the time of analysis will be censored at the time of their last study assessment (for active participants) or at the last date known alive (for participants in follow-up).

9.4.3 Safety Analyses

Unless otherwise specified all safety analyses listed in Table 9 will be based on the safety population. All safety parameters will be analyzed using descriptive statistics, summarized and presented in tables. Data will be summarized by dose and regimen (if applicable) within each part.

Safety will be assessed through summaries of DLTs (for Part A), adverse events, changes in laboratory test results, changes in vital signs and ECGs, and exposure to study treatment.

Table 9 Safety Statistical Analysis Methods

Endpoint	Statistical Analysis Methods
AEs	The original terms recorded on the eCRF by the Investigator for AEs will be coded by the Sponsor.
	For classification purposes, preferred terms will be assigned by the Sponsor to the original terms entered on the eCRF, using the most up-to-date version of the MedDRA terminology for AEs and diseases. AEs will be graded according to NCI CTCAE grades v5.0.
	Adverse events will be summarized by mapped term and appropriate thesaurus level. Toxicity grade, seriousness, and relationship to study treatment will be presented, as well as summaries of deaths, AEs leading to death and premature withdrawal from study treatment. Glossary of AEs, medication, and procedures will be provided.
Nature and frequency of DLTs	DLT events will be presented by individual listings. The MTD will be estimated with a mCRM–EWOC using DLT-evaluable participants. The MTD estimate will be presented along with 90% Credible Intervals.

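### Relating efficacy to ever-positive ADA status, with PFS and OS counted from first dose, builds in guarantee-time bias that tends to favour ADA-positive participants

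*Combined protocol and SAP*

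**What the plan says.** Section 9.4.5 (Immunogenicity Analyses) sets the classification and its use:

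- A baseline-negative participant is positive if they "develop an ADA response following study drug administration (treatment-induced ADA response"). A baseline-positive participant is positive if any later titer rises by a reasonable margin, such as 4-fold. Neither route has a time limit.
- A baseline-negative participant is negative only if they stay so "and all post-baseline samples are negative".
- The period covered is "post-baseline incidence during both the treatment and follow-up periods".
- On the population: "The immunogenicity analyses will include all participants with at least one ADA assessment, irrespective of whether or not the participant receives any treatment". A post-baseline sample is not required.
- On use: "The relationship between ADA status and safety, efficacy, PK, and biomarker endpoints will be analyzed and reported descriptively via subgroup analyses".

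Section 9.4.2 starts the clock at first dose: "PFS will be defined as the time from study treatment initiation (Cycle 1 Day 1"). OS has the same origin.

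In the Schedule of Activities (Section 1.3, Tables 2 and 3), ADA is drawn pre-dose at Cycles 1 to 5. "Thereafter, blood for ADA determination of RO7121661 will be taken at Cycle 7, Day 1, and every 6 cycles afterwards". Both tables also mark ADA at the early termination and safety follow-up visits, and Section 8.5.1 adds: "Additional ADA samples should also be collected at the time of treatment discontinuation or at the safety follow-up visit".

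No landmark, time-varying method, fixed ADA window or minimum number of samples is given for the efficacy comparison.

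**The concern.** The grouping variable is learned after the clock starts. To be classed positive, a participant must be alive at a sample taken after ADA has appeared, and participants who are followed longer give more such samples. Survival time thus helps to decide the group in which it is then counted. This is guarantee-time (immortal-time) bias. A descriptive table or Kaplan-Meier plot carries it just as a test would.

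Section 8.5.1 names loss of efficacy as a possible consequence of ADA. A comparison that tends to flatter ADA positives works against seeing that harm, and could suggest a benefit that does not exist.

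**Working it through.** **No figure to reproduce.** The plan gives no sample size, effect size or error rate for this comparison. The check is therefore on the mechanism and its possible size.

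**Step 1: sampling reach.** With 14-day cycles, the pre-dose samples fall at weeks 0, 2, 4, 6, 8, 12, 24, 36, 48 and so on. The Part B safety follow-up is 90 days (12.9 weeks) after the last dose. Compare three participants:

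- A: last dose at week 6, dies before any off-treatment visit. Last sample at week 6.
- B: last dose at week 6, attends safety follow-up. Last sample at 6 + 12.9 = week 18.9.
- C: last dose at week 48, attends safety follow-up. Last sample at 48 + 12.9 = week 60.9.

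Assume that 40% of participants eventually develop ADA, with exponential onset of median m weeks that is unrelated to outcome. The chance of onset by the last sample, week t, is 40% × (1 − 2^(−t/m)).

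| Median onset m | A (t = 6) | B (t = 18.9) | C (t = 60.9) |
|---|---|---|---|
| 2 weeks | 35.0% | 39.9% | 40.0% |
| 8 weeks | 16.2% | 32.2% | 39.8% |
| 16 weeks | 9.2% | 22.3% | 37.1% |

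The biology is the same for all three, but the chance of the positive label rises with time alive and sampled. Off-treatment samples (B against A) narrow the gap without closing it. Very early onset nearly closes it.

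**Step 2: effect on the hazard ratio.** A null simulation used 200,000 participants per scenario, with ADA onset independent of progression, death and response. It followed the protocol's ADA and scan schedules, including off-treatment samples at 28 and 90 days after last dose. Assumptions not in the documents: median PFS 8 or 16 weeks, eventual incidence 20% or 40%, median onset 2 to 16 weeks, ORR 15%, median post-progression survival 26–30 weeks. Results for median PFS 16 weeks and incidence 40% (true HR 1.00):

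| Median onset | Naive PFS HR | Naive OS HR | Week-8 landmark PFS / OS HR | Time-varying PFS / OS HR |
|---|---|---|---|---|
| 2 weeks | 0.95 | 0.95 | 0.99 / 0.99 | 0.99 / 1.00 |
| 4 weeks | 0.91 | 0.89 | 0.99 / 0.97 | 0.99 / 0.99 |
| 8 weeks | 0.83 | 0.82 | 1.00 / 0.99 | 1.00 / 1.00 |
| 16 weeks | 0.73 | 0.75 | 1.01 / 0.98 | 1.00 / 0.98 |

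Over all scenarios with off-treatment samples, the naive PFS HR was 0.73–0.96 and the OS HR 0.75–0.96. Confirmed ORR was 0.6 to 5.5 points higher in ADA positives. A separate null simulation gave PFS HR 0.81–1.00 and OS HR 0.79–1.00, near 1 only with very early onset. Together the two sets cover assumed median PFS of 8 to 26 weeks.

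**Step 3: does the correction work?** Over all scenarios, the week-8 landmark gave PFS HR 0.98–1.02 and OS HR 0.97–1.00. ADA as a time-varying covariate gave PFS HR 0.99–1.01. For OS it gave 0.98–1.00 with off-treatment samples, but 0.89–1.00 with on-treatment samples only, so the off-treatment results must be used.

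**Step 4: sensitivity to masking.** Further runs assumed 30% incidence and that circulating drug hides some ADA. With half or more hidden, the naive PFS HR could reach or exceed 1 (up to 1.48), while the OS HR stayed at 0.67–0.93. With no masking, the PFS HR was 0.65–0.95; that range includes runs in which few or no off-treatment samples were obtained.

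**The case against.** **It is descriptive and secondary.** No hypothesis test is planned. PFS is summarised only if data suffice, and OS only may be tabulated. Section 9.4.5 says efficacy without naming PFS or OS, and the ADA endpoint in Table 4 is incidence, which the ever-positive rule serves well. All of this stands and limits the importance of the point. It does not remove the bias from any efficacy table or curve split by that status.

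**Positivity does not require staying progression-free or on treatment.** A reader might infer that it does, and that early progressors would almost all be classed negative. The documents do not support this. ADA is sampled at weeks 2, 4 and 6 before the first scheduled scan, again at early termination and safety follow-up, and treatment beyond RECIST progression is allowed (Sections 4.1 and 7.1).

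**A much larger bias is not established.** Detecting ADA only while participants are progression-free, with a constant conversion hazard of 1–3% per week, gives hazard ratios of 0.44–0.61. That omits scheduled off-treatment samples. It also implies that 1 − 0.99^52 = 41% to 1 − 0.97^52 = 79% convert within a year, which nothing in the documents supports.

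**A landmark has its own cost.** Week 8 (Cycle 5 Day 1) lies inside the ±7-day window of the first scan, so scan scheduling would help decide who is still at risk. Part A disease control was 14/39 (35.9%), so many participants may leave near that time. This stands, and it argues for a landmark before the window opens.

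**Conclusion.** The concern holds as a flaw in a stated rule. Following Section 9.4.5 as written compares efficacy between groups that are partly defined by length of survival and sampling. With no true ADA effect and the protocol's full sampling, the naive comparison tends to favour ADA positives, with a PFS HR of about 0.73–1.00 and an OS HR of about 0.75–1.00.

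The size is conditional on the assumed PFS, incidence and onset, and the documents supply none of them. Nor do they give the drug tolerance of the ADA assay, so it would go too far to say that the PFS bias must favour ADA positives. No sample size, error rate or primary endpoint is affected. This is a cheap improvement to an exploratory comparison.

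**What to change.** Keep the ever-positive rule for reporting ADA incidence. For efficacy, add to Section 9.4.5:

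- PFS and OS by ADA status are measured from a pre-specified landmark outside the first-scan window, in participants still at risk, using only samples up to that landmark. Cycle 4 Day 1 (week 6) is suitable: it has a scheduled ADA sample and precedes the scan window (weeks 7 to 9). The simulations used week 8, but the principle is the same: status is fixed before counting starts. Because cycles can be delayed (Section 6.6), state the landmark as a study day.
- Alternatively, ADA enters as a time-varying covariate, using on- and off-treatment samples.
- At least one post-baseline ADA sample is required.
- PFS and OS are not presented by ever-positive status.

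If ORR is also split by ADA, the same landmark status can be used, since it precedes any scheduled response assessment.

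The cost is a few sentences and no new samples. Participants with an event before the landmark, and ADA arising after it, drop out of this one comparison. Neither method removes confounding by prognosis, so the result remains descriptive.
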